3.6. Missing Data and Outliers

3.6.1. Missing Data

In general, missing data will not be imputed unless methods for handling missing data are specified. Exceptions are presented in this document.

Participants with missing outcomes for the primary endpoint due to premature discontinuation from the study will be censored at the Last Study Date defined in Section 3.8.1.

For missing last dosing date of study drug, imputation rules are described in Section 4.2. The handling of missing or incomplete dates for adverse event (AE) onset is described in Section 7.1.5.2, and for prior and concomitant medications in Section 7.4.

3.6.2. Outliers

Outliers will be identified during the data management and data analysis process, but no sensitivity analyses will be conducted. Unless specified otherwise, all data will be included in the data analysis.

3.7. Data Handling Conventions and Transformations

The following conventions will be used for the imputation of date of birth when it is partially missing or not collected:

- If only year of birth is collected, then "01 July" will be imputed as the day and month of birth
- If year of birth is missing, then date of birth will not be imputed.

In general, age collected at Day 1 (in years) will be used for analyses and presented in listings. If age at Day 1 is not available for a participant, then age derived based on date of birth and the Day 1 visit date will be used instead. If an enrolled participant was not dosed with any study drug, the randomization date will be used instead of the Day 1 visit date. For screen failures, the date the first informed consent was signed will be used for the age derivation. Age required for longitudinal and temporal calculations and analyses (eg, estimates of creatinine clearance, age at date of AE) will be based on age derived from date of birth and the date of the measurement or event, unless otherwise specified.

Version 1.0

Non-PK data that are continuous in nature but are less than the lower limit of quantitation (LOQ) or above the upper LOQ will be imputed as follows:

- A value that is 1 unit less than the lower LOQ at the same precision level of the originally reported value will be used to calculate descriptive statistics if the datum is reported in the form of "< x" (where x is considered the lower LOQ). For example, if the values are reported as < 50 and < 5.0, values of 49 and 4.9, respectively, will be used to calculate summary statistics. An exception to this rule is any value reported as < 1 or < 0.1, etc. For values reported as < 1 or < 0.1, a value of 0.9 or 0.09, respectively, will be used to calculate summary statistics.
- A value that is 1 unit above the upper LOQ will be used to calculate descriptive statistics if the datum is reported in the form of "> x" (where x is considered the upper LOQ). Values with decimal points will follow the same logic as above.
- The lower or upper LOQ will be used to calculate descriptive statistics if the datum is reported in the form of "≤ x" or "≥ x" (where x is considered the lower or upper LOQ, respectively).

SARS-CoV-2 viral load results that are below LLOQ but have a positive signal will be reported as "<2228cp/mL SARSCoV2 detected" and those that are below lower limit of detection (LOD) and negative will be reported as "No SARS-CoV2 detected". The data will be imputed as follows:

- A value of 1114 copies/mL (half of the LOQ 2228 copies/mL) will be used to calculate descriptive statistics if the datum is reported as "<2228cp/mL SARSCoV2 detected".
- A value of 746.5 copies/mL (half of the LOD 1493 copies/mL) will be used to calculate descriptive statistics if the datum is reported as "No SARS-CoV2 detected".

SARS-CoV-2 infectious viral titer result will be imputed as follows:

- A value of 100 PFU/mL (half of the LOQ 200 PFU/mL) will be used to calculate descriptive statistics if the datum is reported as "< 200 PFU/mL" and the corresponding qualitative result is "Positive".
- A value of 50 PFU/mL (1/4 of the LOQ 200 PFU/mL) will be used to calculate descriptive statistics if the datum is reported as "< 200 PFU/mL" and the corresponding qualitative result is "Negative".

For baseline SARS-CoV-2 viral load, results of "No SARS-CoV2 detected", "Inconclusive", "<2228cp/mL SARSCoV2 detected" are considered as < LLOQ; numerical results are considered as \ge LLOQ.

Numerical result of SARS-CoV-2 viral load and SARS-CoV-2 infectious viral titer from samples collected with less than specified volume of test solution will not be included in viral load or infectious viral titer analyses. The positive or negative result of these samples will not be impacted.

Any SARS-CoV-2 viral load and infectious viral titer samples collected on or after the day when the participants are receiving additional COVID-19 treatments (see Appendix 3) will be excluded from the viral load or infectious viral titer analysis.

Base 10 logarithm transformation will be used for analyzing SARS-CoV-2 viral load and SARS-CoV-2 infectious viral titer.

Sparse PK concentration values that are below the limit of quantitation (BLQ) will be presented as "BLQ" in the data listing.

Natural logarithm transformation will be used for analyzing concentrations in intensive PK samples from the PK Substudy. Concentration values that are BLQ will be presented as "BLQ" in the concentration data listing. Values that are BLQ will be treated as 0 at predose time points, and one-half the value of the LOQ at postdose time points for summary purposes. Values that are 0 or characters will be excluded from the calculation of geometric means.

The following conventions will be used for the presentation of summary and order statistics for PK concentrations:

- If at least 1 participant has a concentration value of BLQ for the time point, the minimum value will be displayed as "BLQ."
- If more than 25% of the participants have a concentration data value of BLQ for a given time point, the minimum and Q1 values will be displayed as "BLQ."
- If more than 50% of the participants have a concentration data value of BLQ for a given time point, the minimum, Q1, and median values will be displayed as "BLQ."
- If more than 75% of the participants have a concentration data value of BLQ for a given time point, the minimum, Q1, median, and Q3 values will be displayed as "BLQ."
- If all participants have concentration data values of BLQ for a given time point, all order statistics (minimum, Q1, median, Q3, and maximum) will be displayed as "BLQ."

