6.2.1. Analysis of Secondary Efficacy Endpoints

The FAPS will be the primary analysis set for key secondary efficacy endpoints and time to COVID-19 symptom alleviation. The Virology Analysis Set will be the primary analysis set for SARS-CoV-2 nasal swab viral load.

The key secondary endpoints will be tested in the following sequential order using a gatekeeping approach:

- 1. Proportion of participants with all-cause hospitalization by Day 29
- 2. Proportion of participants with COVID-19-related MAVs or all-cause death by Day 29
- 3. Proportion of participants with COVID-19-related MAVs by Day 29
- 4. Proportion of participants with all-cause death by Day 29

The proportion of participants with all-cause hospitalization by Day 29, COVID-19–related MAVs or all-cause death by Day 29, COVID-19 related MAVs by Day 29, and all-cause death by Day 29 will be analyzed in a similar manner to the primary endpoint.

All-cause death by Day 29 will also be compared between the 2 treatment groups using the Fisher's exact test. If a participant prematurely discontinues from the study prior to Day 29 and the death status is missing, the participant will not be included in the analysis.

The Kaplan-Meier product limit method will be used to estimate, and stratified log-rank test will be used to compare the 2 treatment groups for the time to COVID-19 symptom alleviation by Day 15. In addition, a Cox proportional hazards regression model with the stratification factors as covariates will be used to estimate the hazard ratio and its 2-sided 95% CI.

Change from baseline in SARS-CoV-2 nasal swab viral load to each visit including Day 5 will be compared between the 2 treatment groups using a mixed-effects model repeated measures (MMRM) approach. Additionally, change in SARS-CoV-2 viral load from baseline at each postbaseline analysis visit will be provided. Descriptive statistics will be provided by treatment group as follows: (1) Baseline values, (2) Values at each postbaseline analysis visit, (3) Change from baseline at each postbaseline analysis visit. **CCI**

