Proportion of participants with negative SARS-CoV-2 nasal swab viral load at Days 3, 5, 10, and 15	Participants in the Virology analysis set who had SARS-CoV-2 nasal swab collected and nonmissing result of viral load reported at selected visits	Number of participants with negative SARS-CoV-2 nasal swab viral load
Proportion of participants with negative SARS-CoV-2 infectious viral titer at Days 3, 5, 10, and 15	Participants in the Virology analysis set who had SARS-CoV-2 nasal swab collected and nonmissing result of SARS-CoV-2 infectious viral titer reported at selected visits	Number of participants with negative SARS-CoV-2 infectious viral titer

4) Definition of Hospitalization

MAVs type of Emergency Room, non-ICU Hospitalization, ICU Hospitalization, and Hospitalization (unknown ward) could meet criteria for hospitalization if one of the following conditions is met:

- If the duration of the MAV is greater than 24 hours.
- If the duration is missing and end date of the MAV is 1 day after the start date.

Time to hospitalization is calculated as Start date of Hospitalization – First dose date + 1.

5) SARS-CoV-2 positive at baseline

SARS-CoV-2 positive at baseline is defined as test result from central lab.

- Cepheid's Xpert Xpress CoV-2/Flu/RSV plus (Multiplex) test result is positive for SARS-CoV-2 or
- SARS-CoV-2 RT-qPCR test result is numerical viral load result or "<2228cp/mL SARSCoV2 detected", regardless the sample was collected with less than specified volume of test solution.

GS-US-611-6273-Final Analysis-SAP-v1.0

ELECTRONIC SIGNATURES

Signed by	Meaning of Signature	Server Date (dd-MMM- yyyy hh:mm:ss)
PPD	Biostatistics eSigned	24-Jan-2024 01:01:34
PPD	Global Development Lead (GDL) eSigned	24-Jan-2024 17:55:34

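### SAP 3.7 excludes only the numerical results of under-volume swabs; taken literally, their below-limit results stay in as low imputed values and within-arm viral load decline is slightly overstated

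*SAP*

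**What the plan says.** SAP 3.7 (Data Handling Conventions and Transformations) states that numerical results "from samples collected with less than specified volume of test solution will not be included in viral load or infectious viral titer analyses", and adds: "The positive or negative result of these samples will not be impacted".

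The same section imputes the two kinds of below-limit PCR result:
- Detected but below the LLOQ: "A value of 1114 copies/mL (half of the LOQ 2228 copies/mL) will be used to calculate descriptive statistics".
- Not detected: "A value of 746.5 copies/mL (half of the LOD 1493 copies/mL) will be used to calculate descriptive statistics".

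Neither rule has an exception for under-volume samples.

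Two places show how the SAP uses the word numerical. For baseline viral load, SAP 3.7 classes not-detected, inconclusive and detected-below-LLOQ results as below the LLOQ, while "numerical results are considered as" at or above it. SAP Appendix 3, item 5, defines a positive baseline PCR as: "SARS-CoV-2 RT-qPCR test result is numerical viral load result or" the detected-below-LLOQ result, "regardless the sample was collected with less than specified volume of test solution". In both, numerical is a separate category from a below-limit text result.

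SAP 3.6.2, under the outlier heading, includes all data unless otherwise specified. SAP 6.2.1 compares "Change from baseline in SARS-CoV-2 nasal swab viral load to each visit including Day 5" between arms by MMRM in the Virology Analysis Set, and also reports values and changes by arm at each visit.

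**The concern.** A short-volume swab makes the quantity unreliable whatever the reading. An exclusion that depends only on volume does little harm if volume is unrelated to viral load. An exclusion that also depends on the reading is different. Taken literally, a short-volume Day 5 swab reading 5 log10 copies/mL is dropped, while one reading not detected stays in as 2.87 log10. High values are lost, low values are kept, and the arm mean moves down.

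The selection acts only after baseline. The Virology Analysis Set (SAP 3.1.4) requires a baseline at or above the LLOQ, so no low imputed baseline enters to offset the shift. An excluded under-volume baseline value simply costs that participant's change score. At stake are the by-arm viral load values and declines that SAP 6.2.1 will report and, to a much smaller degree, the MMRM contrast. The same wording governs infectious titer.

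**Working it through.** **1. The plan's own figures.** 2228/2 = 1114 and 1493/2 = 746.5, as stated. On the log10 scale the LLOQ is 3.348, the LOD 3.174, and the imputed values 3.047 and 2.873.

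**2. Formula.** Let u be the share of under-volume samples (unrelated to viral load), q the share of Day 5 results that are quantified, mq the mean log10 of those, and ml the mean of the imputed values.

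- Mean of all samples: q·mq + (1−q)·ml
- Mean when only quantified under-volume results are dropped: [q(1−u)·mq + (1−q)·ml] / (1−uq)
- Difference: −u·q(1−q)(mq−ml) / (1−uq)

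If every under-volume result is dropped, the difference is 0.

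**3. Assumed inputs.** The documents give neither u nor a Day 5 distribution. I take Day 5 log10 viral load as normal with SD 1.5 and means 3.8 (placebo) and 3.3 (drug).

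- Placebo: q = 1−Φ((3.348−3.8)/1.5) = 0.618; mq = 4.725; ml = 2.893
- Drug: q = 1−Φ((3.348−3.3)/1.5) = 0.487; mq = 4.527; ml = 2.889

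At u = 10%:
- Placebo: 0.1 × 0.618 × 0.382 × 1.832 / 0.938 = 0.046
- Drug: 0.1 × 0.487 × 0.513 × 1.638 / 0.951 = 0.043

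| u | Fall in placebo mean | Fall in drug mean | Shift in drug minus placebo |
|---|---|---|---|
| 5% | 0.022 | 0.021 | +0.001 |
| 10% | 0.046 | 0.043 | +0.003 |
| 20% | 0.099 | 0.091 | +0.008 |
| 30% | 0.159 | 0.144 | +0.015 |

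The full-data difference on these inputs is −0.338, so a positive shift is towards the null.

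**4. Other inputs.** With q from 0.3 to 0.95, mq from 4.5 to 5.5 and ml = 2.96 (midpoint of the two imputed values), the arm mean falls by:

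- 0.001 to 0.006 at u = 1%
- 0.004 to 0.033 at 5%
- 0.008 to 0.067 at 10%
- 0.018 to 0.141 at 20%

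At mq = 5 in both arms, over several pairs of q, the contrast shifts by −0.007 to +0.004 at u = 5% and by −0.033 to +0.022 at 20%. It does not shift if q is equal. The sign is therefore not fixed.

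**5. Simulation check.** I assumed 2 million participants per arm, baseline mean 6.0 (SD 1.2), Day 5 means 4.0 and 4.4 (SD 1.4) and correlation 0.5. At u = 10%:

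| Handling | Drug-arm mean change | Arm difference |
|---|---|---|
| All samples | −1.879 | −0.336 |
| Only quantified under-volume results dropped | −1.900 | −0.337 |
| All under-volume results dropped | −1.878 | −0.336 |

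The fix removes the shift to within simulation error.

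**6. Unequal rates.** With the same viral load distribution in both arms and u of 20% against 5%, the inputs of step 3 give a false difference of 0.099 − 0.022 = 0.077 from the rounded table (0.076 unrounded) for the placebo distribution, or 0.091 − 0.021 = 0.070 for the drug distribution.

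**The case against.** **The rule may mean something else.** The SAP never says that a below-limit result from a short-volume swab enters a mean or the MMRM. The two sentences can be read as quantity against call: drop the number, keep the positive or negative status. There are clear uses for that status, namely baseline positivity for the FAPS and the proportion-negative endpoints. For titer, SAP 3.7 pairs each below-limit datum with a separate qualitative result. The SAP 3.7 sentence on numerical results also concerns baseline classification only. This reading is possible, and under it the bias is nil. It is not the natural one: Appendix 3 draws the same distinction, the imputation rules have no exception, and the next paragraph of SAP 3.7, on additional COVID-19 treatment, excludes whole samples.

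**Entry into the MMRM is inferred.** The imputed values are specified for descriptive statistics, and the SAP does not say what represents a below-limit result in the model. This stands.

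**Complete-case means overstate the effect on the MMRM.** The model also uses the other visits. An approximate likelihood-type check (regression on baseline and Day 3; assumed baseline 6.0, Day 3 means 4.9 and 4.6, correlations 0.3 to 0.7) lowers the arm shift at 10% to 0.02 to 0.04 log10. The contrast moves by 0.002 or less at 10% and 0.006 or less at 20%. This stands too.

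**A reader might infer that the drug effect is overstated.** The documents do not support that. Both arms shift the same way, and on the inputs of step 3 the contrast moves against the drug. The false difference in step 6 needs a fourfold gap in collection quality between arms. The trial is randomized and double-blind, and study personnel take the swabs. Differences between sites balance across arms in expectation.

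**Conclusion.** The point holds as a wording defect with a small, conditional bias. On the natural reading, exclusion of under-volume post-baseline swabs depends on the result, and the reported within-arm decline is too large: about 0.02 log10 at an assumed 5% rate and 0.04 to 0.05 at 10%, for complete-case means under the stated normal distributions. With equal rates, the contrast moves by about 0.02 log10 or less on those inputs, towards the null. Other inputs can reverse the sign and reach about 0.03 at a 20% rate.

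Three limits apply. The true rate is unknown, so the practical effect may be negligible. The alternative reading gives no bias. Day 5 viral load is listed among the other secondary endpoints (SAP 6.2), outside the gatekeeping sequence of SAP 3.5, so no confirmatory claim rests on it. It would go too far to state as fact that high viral loads are deleted selectively: that follows from one reading of the rule, not from an explicit statement.

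**What to change.** Replace the two sentences in SAP 3.7 with wording to this effect: samples collected with less than the specified volume are excluded from every quantitative viral load and infectious titer analysis (descriptive statistics, change from baseline, MMRM) whatever the result, including values imputed below the LLOQ or LOD; their positive or negative status is kept for the FAPS definition and the negativity endpoints. Report the number of such samples by arm and visit, so that a reader can judge both the rate and its balance.

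The cost is one sentence, one programming filter and a few more missing post-baseline values. If whole-sample exclusion was always intended, the change only removes a programming risk. SAP Section 1 provides for changes after finalization to be documented in the CSR.

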6.4. Intercurrent Events

Handling of intercurrent events for the efficacy endpoints related to hospitalization, MAVs, death, symptom alleviation, SARS-CoV-2 viral load, or SARS-CoV-2 infectious viral titer are shown in Table 6-1. Intercurrent events are events occurring after treatment initiation that affect either the interpretation or the existence of the measurement of an endpoint. An event (eg, use of rescue medication) that occurs after an endpoint of interest (eg, hospitalization) is not considered as an intercurrent event.

Endpoint	Intercurrent event	Strategy	Description		
Proportion of COVID-19–related hospitalization or all-cause death by Day 29 Proportion of participants with all-cause hospitalization by Day 29	Discontinue randomized treatment prior to endpoint (due to AE, lack of efficacy, investigator's discretion, noncompliance with study drug, protocol violation, participant decision, lost to follow-up)	Treatment policy	Ignore the occurrence of intercurrent events (use observed outcome)		
Proportion of participants with COVID-19–related MAVs or all-cause death by Day 29 Proportion of participants with COVID-19–related MAVs by Day 29	Use of rescue medication	Treatment policy	Ignore the occurrence of intercurrent events (use observed outcome)		
Proportion of participants with all-cause death by Day 29					

Table 6-1.Handling of Intercurrent Events

Endpoint	Intercurrent event	Strategy	Description		
	Hospitalization for the treatment of COVID-19 or all-cause death	Composite policy	Hospitalization for the treatment of COVID-19 or all-cause death means never achieve symptom alleviation (censored at Day 14)		
Time to COVID-19 symptom alleviation by Day 15	Discontinue randomized treatment prior to symptom alleviation (due to AE, lack of efficacy, investigator's discretion, noncompliance with study drug, protocol violation, participant decision, lost to follow-up)	Treatment policy	Ignore the occurrence of intercurrent events (use observed outcome)		
	Use of rescue medication	Composite policy	Use of rescue medication means never achieve symptom alleviation (censor at Day 14)		
	Hospitalization for the treatment of COVID-19 or all-cause death	Treatment policy	Ignore the occurrence of intercurrent events (use observed outcome)		

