Proportion of participants with negative SARS-CoV-2 nasal swab viral load at Days 3, 5, 10, 15 Proportion of participants with negative SARS-CoV-2 nasal swab infectious viral titer at Days 3, 5, 10, 15	Discontinue randomized treatment prior to endpoint (due to AE, lack of efficacy, investigator's discretion, noncompliance with study drug, protocol violation, participant decision, lost to follow-up)	Treatment policy	Ignore the occurrence of intercurrent events (use observed outcome)		
,	Use of rescue medication	Composite policy	Use of rescue medication means never achieve negativity		

AE = adverse event; COVID-19 = coronavirus disease 2019; MAVs = medically attended visits

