- For participants with missing time of first dose, missing time is imputed using the time of SIC questionnaire assessment on the first dose date or 12:00 whichever occurs first.
- 4. Additional censoring rules due to Intercurrent event:

Hospitalization for the treatment of COVID-19 or all-cause death or Use of rescue medication (see definition in #2)

Date and Time of Day 14 SIC questionnaire assessment – Date and time of first dose.

Use Day 14 23:59 if no Day 14 SIC questionnaire assessment.

2) COVID-19 Rescue Medications

Details of COVID-19 rescue medications are provided in the table below.

Drug Class	Dictionary Level	Prohibited PREF Codes	Prohibited Ingredient, PREF, and/or ATC Decodes	
Bamlanivimab and Etesevimab	PREF	15665101001	BAMLANIVIMAB;ETESEVIMAB	
Bamlanivimab	PREF	15343501001	BAMLANIVIMAB	
Bamlanivimab	PREF	15665101001	BAMLANIVIMAB;ETESEVIMAB	
Casirivimab and Imdevimab	PREF	15585401001	CASIRIVIMAB;IMDEVIMAB	
Cilgavimab and Tixagevimab	PREF	15616901001	CILGAVIMAB;TIXAGEVIMAB	
Molnupiravir	PREF	15326101001	MOLNUPIRAVIR	
Nirmatrelvir and Ritonavir	PREF	15892101001	NIRMATRELVIR;RITONAVIR	
Remdesivir	PREF	14269001001	REMDESIVIR	
Sotrovimab	PREF	15464401001	SOTROVIMAB	
Bebtelovimab	PREF	16033001001	BEBTELOVIMAB	
Ensitrelvir	PREF	16350701001	ENSITRELVIR	
Ensitrelvir	PREF	16350702001	ENSITRELVIR FUMARIC ACID	

ATC = anatomical therapeutic chemical; PREF = preferred

Additional medication may be included during final review of concomitant medications prior to data finalization.

3) Population, denominator, and numerator for efficacy endpoints summaries of proportion

Endpoint / Summary	Population / Denominator	Numerator
Proportion of COVID-19-related hospitalization or all cause death by Day 29 Proportion of participants with all-cause hospitalization by Day 29 Proportion of participants with COVID-19-related MAVs or all-cause death by Day 29 Proportion of participants with COVID-19-related MAVs by Day 29 Proportion of participants with all-cause death by Day 29	FAPS Based on KM estimate, no explicit denominator used	Total number of events by selected visits Note: Proportions from KM estimate differ from proportion calculated directly from number of event and participants at risk

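### After rescue medication, the visible SAP text gives two different denominators for the viral load and infectious titer negativity proportions

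*SAP*

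**What the plan says.** Three places in the SAP bear on a participant who takes rescue medication before a swab visit.

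- **Section 3.7 (data handling).** A swab taken once additional COVID-19 treatment has begun, that same day included, "will be excluded from the viral load or infectious viral titer analysis". The rule covers any such sample. The paragraph just before it deals with low-volume samples. It drops only their numerical result and adds: "The positive or negative result of these samples will not be impacted". The rescue rule has no such reservation.
- **Table 6-1 (Section 6.4).** For "Proportion of participants with negative SARS-CoV-2 nasal swab viral load at Days 3, 5, 10, 15", and for the matching infectious titer endpoint, rescue is handled by a composite strategy: "Use of rescue medication means never achieve negativity".
- **Appendix 3 item 3.** The viral load negativity denominator is made up of Virology Analysis Set participants with a swab collected and a "nonmissing result of viral load reported at selected visits". The titer row is worded in parallel.

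The trigger appears to be the same for the first two. Section 3.7 points to Appendix 3, and the only such list there is item 2: "Details of COVID-19 rescue medications are provided in the table below". No visible passage says which rule takes precedence for the negativity endpoints, or whether a rescued participant without a usable swab stays in the denominator.

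**The concern.** A composite strategy works only if participants with the intercurrent event stay in the analysis as failures. If the Section 3.7 exclusion is applied when the analysis dataset is built, a rescued participant has no analysable result at later visits. The Appendix 3 denominator then removes that participant. A rescued participant with no swab at the visit is removed by Appendix 3 alone. This can easily happen, because the schedule of assessments allows virtual visits on Days 3, 10 and 15, when no swab is taken.

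Two programmers working carefully from the same SAP could therefore report different proportions. One set would match the strategy in Table 6-1. The other would be a proportion among non-rescued participants, which answers a different question from the one Table 6-1 states.

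**Working it through.** The documents give no expected negativity or rescue rate for these endpoints, so there is no figure to reproduce. The check is a comparison of the two readings, with assumed rates.

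**Notation, for one arm at one visit**
- r = share rescued on or before the visit (not in the documents; assumed 1% to 10%).
- p = proportion negative among those not rescued (not in the documents; assumed 10% to 90%).
- For simplicity, every non-rescued participant has a swab result.

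**Numerator.** Neither reading uses a post-rescue swab to count a participant as negative. The count of negatives is N x (1 - r) x p in both.

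**Denominator**
- Section 3.7 with Appendix 3 read strictly: rescued participants leave, so N(1 - r). Proportion = p.
- Table 6-1 composite: rescued participants stay as failures, so N. Proportion = p(1 - r).
- Gap in the arm = p - p(1 - r) = p x r.

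**Numbers, assuming 500 participants in the arm**

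| p | r | Rescued dropped | Rescued kept as failures | Gap (points) |
|---|---|---|---|---|
| 30% | 2% | 147/490 = 30.0% | 147/500 = 29.4% | 0.6 |
| 60% | 5% | 285/475 = 60.0% | 285/500 = 57.0% | 3.0 |
| 90% | 10% | 405/450 = 90.0% | 405/500 = 81.0% | 9.0 |

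At the low end of the assumed ranges (p = 10%, r = 1%) the gap is 0.10 x 0.01 = 0.1 points.

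A third reading is possible: Appendix 3 keeps rescued participants who have a swab and drops those who do not. Its result lies between the two columns.

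**Between arms** (A = GS-5245, P = placebo)
- Dropped: pA - pP.
- Kept: pA(1 - rA) - pP(1 - rP).
- Kept minus dropped = pP x rP - pA x rA, whose sign depends on all four rates.

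Three assumed cases:
- p = 60% in both arms, rescue 1% on A and 5% on P. Dropped: 0. Kept: 0.60 x (0.05 - 0.01) = 2.4 points.
- p = 60% on A and 40% on P, rescue 4% on A and 5% on P. Dropped: 20.0 points. Kept: 0.60 x 0.96 - 0.40 x 0.95 = 0.576 - 0.380 = 19.6 points.
- p equal and r equal in both arms. Difference 0 under both readings, although each arm's proportion still shifts by p x r.

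**The case against.** The strongest reply is that the rules can be read together. Discarding a post-rescue swab value and scoring the participant as not negative are compatible, because the composite rule does not need the value. A reader might infer that Section 3.7 and Table 6-1 cannot both be applied; the text does not support that. Section 3.7 excludes a sample from an analysis and does not say that its result becomes missing. Appendix 3 asks for a swab collected and a result reported, and a rescued participant with a swab could meet both conditions.

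Context also favours a numerical-only reading of Section 3.7. The preceding paragraph uses nearly the same phrase for numerical results, and the next one sets the log10 transformation. Table 6-1 is the endpoint-specific rule. The revision log shows that its SARS-CoV-2 entries were added in Version 1.0 to clarify handling, and a specific rule would normally prevail over a general convention. Finally, the section that would analyse these endpoints appears to be redacted between 6.2.1 and 6.4, and it may settle the matter.

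Much of this stands. The numerical-only reading is plausible and probably intended. But it has to be inferred: the reservation for positive or negative status is written for low-volume samples and not for post-rescue samples. Section 6.4 itself presents the negativity endpoints as related to "SARS-CoV-2 viral load, or SARS-CoV-2 infectious viral titer are shown in Table 6-1". Even on the favourable reading, the visible text does not place a rescued participant who has no swab.

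A reader might also infer from Section 6.4 that Table 6-1 lacks a needed row for change in viral load at Day 5. That is only a matter of presentation: Section 3.7 already gives that endpoint one clear rule, so nothing conflicts.

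**Conclusion.** The point holds for the denominator of the two negativity endpoints. On the visible text, Section 3.7 and Appendix 3 taken literally can drop participants whom Table 6-1 keeps as failures, and nothing states which applies. The effect on an arm's proportion is p x r: 3.0 points at an assumed 60% negative and 5% rescued, and 0.1 to 9.0 points over the assumed ranges.

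Three limits apply.

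- **Rates.** Every rescue and negativity rate used here is an assumption. The documents suggest that rescue may be limited: Protocol Section 4.3 excludes people expected to obtain and use authorized therapies within 5 days of randomization, and SAP Section 7.4.2 summarizes rescue use only if there are enough data.
- **Direction.** A reader might infer that dropping rescued participants always pulls the comparison toward no difference. The second between-arm case shows otherwise: with slightly more rescue on placebo, dropping gives 20.0 points and keeping gives 19.6.
- **Reach.** The negativity endpoints are not among the primary, key secondary or other secondary endpoints listed in SAP Sections 6.1 and 6.2. No alpha-controlled test is touched.

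This is a modest inconsistency. It is worth correcting because the reported proportions should match the stated strategy, and the correction is cheap.

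**What to change.** Make two edits.

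1. **Section 3.7.** State that the exclusion of samples taken on or after the day of additional COVID-19 treatment applies to numerical viral load and titer analyses only, and that the negativity endpoints follow Table 6-1.
2. **Appendix 3 item 3.** For both negativity rows, state that a participant with rescue medication on or before the visit stays in the denominator and counts as not negative, with or without a swab at that visit. Results from visits before rescue are used as observed, which agrees with Section 6.4. The phrase on or before the visit also matches the same-day trigger in Section 3.7.

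The cost is about one sentence in each place and one derivation rule, with no new data. Version 1.0 is final, and the SAP Introduction sends later changes to the clinical study report, so the rule used should at least be recorded there. If the redacted section already states it, a cross-reference from Section 3.7 and Appendix 3 is enough.
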